5.3.2.6 Urinalysis

Urinalysis will be performed locally at the Screening visit, at C1D1 (within 72 hours prior to study drug administration), at D1 of all subsequent cycles, and at the End of Treatment visit.

Urinalysis should consist of specific gravity, pH, glucose, protein, ketones, and blood. If clinically indicated, some or all of these tests may be repeated on other study days.

5.3.2.7 Pregnancy testing

Women of child-bearing potential must have a negative hCG at Screening and within 72 hours prior to dosing at C1D1. Subsequently, serum pregnancy testing will be performed prior to study drug dosing on D1 of every cycle, at the End of Treatment visit, and serum or urine pregnancy testing will be performed monthly thereafter for 150 days following the last administration of study treatment.

Pregnancy testing after the end of treatment may be performed at the patient's local gynecologist to reduce the burden related to study visits at the site, but must be communicated to the study Investigator.

The Investigator may conduct additional pregnancy tests (serum or urine) to confirm the absence of pregnancy at any time during the study. If a pregnancy test result is positive, study drug must be discontinued, the patient followed for safety, and the outcomes of the pregnancy assessed (see Section 7.4.5). Further details regarding the risk of pregnancy are provided in Section 7.1.3.

5.3.2.8 *Adverse event monitoring*

AEs will be monitored throughout the study and graded in severity according to the guidelines outlined in NCI CTCAE 5.0.

Please refer to Section 7 for details regarding AE collection and management.

5.3.2.9 *Concomitant medications*

Any medications or significant non-drug therapies (including herbal medicines) that are taken by or administered to the patient during the course of the study (until the safety follow-up visit at Day 28 for all patients, and Day 90 for patients receiving derazantinib-atezolizumab in combination) must be recorded in the eCRF including the dosage, frequency of administration, route of administration, therapeutic indication, and start/stop dates of use.

5.3.3 *Efficacy assessments*

5.3.3.1 *Tumor imaging and assessment of disease*

The process for image collection and transmission to the central imaging vendor is provided in the Imaging Charter. Tumor disease assessments should comprise the chest, abdomen, and pelvis. Tumor imaging should be acquired by computed tomography (CT, strongly preferred). Magnetic resonance imaging (MRI) should be used when CT is contraindicated, and for imaging in the brain.

A bone scan (BS) – alternatively, a whole-body MRI (WBMRI) - should also be performed at Screening only in patients with new symptoms (e.g., new persistently elevated ALP) to assess bone metastasis; screening of asymptomatic patients for clinically unapparent bone metastases is not supported by applicable guidelines (Witjes 2018) but may be done at the Investigator's discretion if local routine practice. Patients with positive BS/WBMRI at baseline will undergo further radiologic assessments of bone lesions performed at protocol-scheduled time points for tumor assessments and as per institutional practice. Lytic/mixed lesions with soft tissue component may be included in the evaluation of disease burden if it meets measurability criteria while blastic lesions are considered non-measurable, in accordance with RECIST 1.1.

The same imaging technique regarding modality and use of contrast should be used in a patient throughout the study.

Local site Investigator/radiology assessment based on RECIST 1.1 will be used to determine patient eligibility. All measurable and evaluable lesions should be assessed and documented by the site study team at the Screening visit.

All scheduled images for all study patients must be submitted to the central imaging vendor. Additional imaging (including other modalities) obtained at unscheduled time points to determine disease progression, as well as imaging obtained for other reasons, but which captures radiologic progression, must also be submitted to the central imaging vendor.

5.3.3.2 Tumor measurement and response evaluations

Tumor imaging assessments (CT/MRI of the chest, abdomen, and pelvis, plus a BS/WBMRI, if applicable) must be done at the time of the Screening visit. However, if an assessment has been performed for routine clinical management after administration of the last dose of any prior anti-tumor treatment, but prior to obtaining informed consent and within 28 days of first dose of study treatment on C1D1, then this may be used for Screening purposes; in such situations it is not necessary to repeat tests if the assessments are of sufficient diagnostic quality.

5.3.3.2.1 Initial tumor imaging

For initial tumor imaging at Screening, the site study team must review Screening images to confirm the patient has measurable disease per RECIST 1.1.

5.3.3.2.2 On-treatment tumor imaging

Study imaging assessments consist of CT/MRI of the chest, abdomen, and pelvis (plus a BS/WBMRI, if applicable). The first on-study tumor imaging assessments will be performed after 9 weeks on study, and will be repeated every 9 weeks from C1D1 (± 7 days) (approximately every 3 cycles, i.e., at C4, C7, C10) or more frequently if clinically indicated. After 27 weeks (9 cycles), the assessment interval is every 12 weeks (± 7 days, i.e. at C14, C18, etc.) for all patients. Imaging timing should be based on the first dose at C1D1, should follow calendar days, and should not be adjusted for delays in cycle starts.

Results of all on-treatment tumor imaging assessments must be reviewed by the Investigator before dosing at the next cycle.

5.3.3.2.3 Post-treatment tumor imaging

Patients who discontinue study treatment should have a tumor evaluation visit as soon as possible after the event (e.g., clinical deterioration; ± 4 -week window). If a previous scan was obtained within 4 weeks prior to the End of Treatment Visit, then a scan is not mandatory. For patients who discontinue study treatment without documented radiologic disease progression, every effort should be made to perform radiologic imaging. For patients who discontinue study treatment due to documented PD, this is the final required tumor imaging.

5.3.3.2.4 RECIST 1.1 and iRECIST

The efficacy of derazantinib monotherapy treatment and derazantinib-atezolizumab in combination will be primarily measured by ORR evaluated by BICR using RECIST 1.1 (see [Appendix 2](#)).

In addition, an exploratory assessment will be performed using iRECIST criteria ([Seymour 2017](#)) in patients treated with derazantinib-atezolizumab in combination, including those patients undergoing crossover treatment (see [Appendix 3](#) for comparison of RECIST 1.1 and iRECIST).

The iRECIST criteria is RECIST 1.1 adapted to account for the tumor response patterns seen with immunotherapeutic drugs. In patients undergoing combination treatment with derazantinib and atezolizumab, iRECIST will be used by the site Investigator / local

radiology review to assess tumor response and progression, and to make treatment decisions. These data will be collected in the clinical database. Treatment efficacy based on iRECIST as assessed by central imaging vendor review will be evaluated retrospectively.

The Investigator should make every attempt to perform the confirmation scan of CR or PR 4–5 weeks after the last scan was performed. The confirmation scan of iUPD should be performed 4–8 weeks after the last scan was performed, unless criteria for clinical stability are not met (see below).

5.3.3.2.5 Management of immunotherapy-treated unconfirmed disease progression

In patients treated with derazantinib-atezolizumab in combination¹ who have iUPD (i.e., initial evidence of radiological PD by RECIST 1.1 as verified by the central imaging vendor), it is at the discretion of the Investigator whether to continue a clinically stable patient (as defined below) on study treatment until repeat imaging is obtained. For patients with iUPD, confirmation is done on the basis of observing any of the following scenarios in clinically stable patients:

- Worsening of existing target lesion(s)
- Worsening of existing non-target lesion(s)
- Development of new lesions(s)

If progression is confirmed by a CT/MRI after 4–8 weeks, the patient should discontinue study treatment.

If progression is not confirmed and criteria of iCR, iPR, or iSD are met compared with baseline (i.e. a reduction in lesion diameter is shown compared to the iUPD assessment), then subsequent assessment are to be compared against the tumor diameter nadir values of iCR, iPR, or iSD. If iUPD occurs again (compared with nadir values of iCR, iPR, or iSD) then iUPD is again to be confirmed (by further growth) at the next assessment for iCPD to be assigned.

If no change in tumor size or extent from iUPD occurs, then the timepoint response would again be iUPD. This approach allows atypical responses, such as delayed responses that occur after pseudo-progression, to be identified (Seymour 2017). Patient management using iRECIST is detailed in Table 3.

This clinical judgment decision by the Investigator should be based on the patient's overall clinical condition, including performance status, clinical symptoms, and laboratory data. Patients may continue to receive study treatment and tumor assessment should be repeated 4–8 weeks later in order to confirm iUPD by iRECIST per site assessment.

Clinical stability is defined as the following:

¹ Applicable to patients receiving derazantinib-atezolizumab in combination in Substudies 3 and 4, including patients in Cohorts 3a and 4a crossing over from derazantinib monotherapy after centrally confirmed radiographic PD per RECIST 1.1

- 1) Absence of symptoms and signs indicating clinically significant progression of disease, including worsening of laboratory values, and
- 2) No decline in ECOG PS, and
- 3) Absence of rapid PD, and
- 4) Absence of progressive tumor at critical anatomical sites (e.g., cord compression) requiring urgent alternative medical intervention

Any patient deemed clinically unstable should be discontinued from study treatment at site-assessed first radiologic evidence of PD, and is not required to have repeat imaging for PD confirmation.

In determining whether or not the tumor burden has increased or decreased per iRECIST, the Investigator should consider all target and non-target lesions, as well as any incremental new lesion(s).

Table 3 Imaging and treatment after first radiologic evidence of PD if iRECIST is followed

Imaging assessment	Clinically stable		Clinically unstable	
	Imaging	Treatment	Imaging	Treatment
First evidence of iUPD	Repeat imaging at 4–8 weeks to confirm PD (iCPD)	May continue study treatment at the local site Investigator’s discretion while awaiting confirmatory tumor imaging by site by iRECIST.	No repeat imaging	Discontinue
Repeat tumor imaging results in iCPD at the local site	No further repeat imaging	Withdraw from study treatment	Not applicable	
Repeat tumor imaging shows iSD, iPR or iCR by local site	Continue regularly scheduled imaging assessments	Continue study treatment at the local site Investigator’s discretion	Not applicable	

Abbreviations: PD, progressive disease; iUPD, unconfirmed progressive disease; iCPD, confirmed progressive disease; iSD, stable disease; iPR, partial response; iCR, complete response; iRECIST, Response Evaluation Criteria In Solid Tumors (adapted to account for the unique tumor response seen with immunotherapeutic drugs).

5.3.4 Pharmacokinetic assessments

The collection, storage, and shipping of blood samples will be performed as described in the Laboratory Manual.

5.3.4.1 Pharmacokinetic assessments for derazantinib

Blood samples will be taken to determine the PK parameters of derazantinib. Exploratory assessments of metabolites of derazantinib may also be investigated from the same samples.

PK blood sampling for derazantinib will be performed according to a rich PK schedule or a sparse PK schedule.

5.3.4.1.1 *Overview of specific PK sampling requirements*

All patients, excluding SIA patients in Substudies 3 and 5, will undergo sparse PK sampling for measurement of derazantinib plasma concentrations. These samples may also be used for exploratory metabolite identification and/or quantification of metabolites.

All **SIA patients in Substudies 3 and 5** will undergo rich PK sampling for measurement of plasma concentrations of derazantinib and relevant PK parameters.

Additionally, in **Substudy 3, Cohort 4b and Crossover**, PK sampling of atezolizumab and ADAs will be performed.

5.3.4.1.2 *Rich PK profiling*

Rich PK profiling will be performed for all **SIA patients in Substudies 3 and 5**, and will be drawn in accordance with the following schedule¹:

- C1D1, prior to derazantinib dose, and 1 hour (± 5 minutes), 2 hours (± 5 minutes), 4 hours (± 15 minutes), 8 hours (± 30 minutes), 10 hours (± 30 minutes), 12 hours (± 30 minutes; prior to the second dose administration), 24 hours after first derazantinib administration (i.e., 12-hour post second dose administration but within 1 hour prior to the third dose).
- C1D8, pre-dose (within 1 hour prior to the next dose), and 6–8 hours after derazantinib administration.
- C1D15, pre-dose (within 1 hour prior to the next dose), and 6–8 hours after derazantinib administration.
- C2D1, prior to derazantinib (within 1 hour prior to the next dose), and 1 hour (± 5 minutes), 2 hours (± 5 minutes), 4 hours (± 15 minutes), 8 hours (± 30 minutes), 10 hours (± 30 minutes), 12 hours (± 30 minutes; prior to the second dose administration), 24 hours after derazantinib administration (i.e., 12-hour post previous dose administration but within 1 hour prior to the next dose).
- C2D8, pre-dose (within 1 hour prior to the next dose), and 6–8 hours after derazantinib administration.
- C2D15, pre-dose (within 1 hour prior to the next dose), and 6–8 hours after derazantinib administration.
- C3D1, prior to derazantinib (within 1 hour prior to the next dose), and 6–8 hours after derazantinib administration.
- C4D1, prior to derazantinib administration (within 1 hour prior to the next dose).
- 28-day Safety Follow-up visit

5.3.4.1.3 *Sparse PK sampling*

Sparse PK profiling will be performed for all patients (excluding SIA patients in Substudies 3 and 5), according to the following schedule:

¹ This schedule may be adapted to locally applicable clinical routine with the agreement of the Sponsor.

- C1D1 and C1D15, prior to derazantinib (within 1 hour prior to the next dose), and 6–8 hours after the study drug administration.
- C2D1, prior to derazantinib (within 1 hour prior to the next dose)
- C3D1, prior to derazantinib (within 1 hour prior to the next dose), and 6–8 hours after the study drug administration.
- C4D1, prior to derazantinib administration (within 1 hour prior to the next dose)
- 28-day Safety Follow-up visit

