1.4.3.1 Derazantinib

In clinical studies, the maximum tolerated dose of derazantinib monotherapy was assessed, and the RP2D was determined as continuous daily oral administration of 300 mg derazantinib (Papadopoulos 2017). In a Phase 2 study, derazantinib demonstrated encouraging anti-tumor activity and a manageable safety profile in patients with advanced, unresectable iCCA with *FGFR2* fusion who progressed after chemotherapy (Mazzaferro 2019).

Based on the data from completed and ongoing clinical studies with derazantinib, the most commonly reported drug-related adverse events (AEs) are transaminases elevations, fatigue /asthenia, gastrointestinal side effects (nausea, vomiting, diarrhea, constipation), xerostomia, hyperphosphatasemia, dysgeusia, decreased appetite, ocular side effects (xerophthalmia and blurred vision) and alopecia (see Section 7.1.1). Adverse events reported in derazantinib-treated patients have largely been mild to moderate in severity, and have infrequently required concomitant treatments (e.g., phosphate reducing agents) or study drug discontinuation.

New clinical pharmacology data from a food-effect study (Study DZB-CS-103) and from a mass balance study (Study DZB-CS-102) became available and simulations from a new two-compartment population PK model, which included data from these two new studies and from a previous clinical Phase 1 study (Study ARQ 087-101), was completed recently. The data from these analyses suggest that the half-life of derazantinib is in a range of 8 to 10 days compared to a previous assumption of only 5 days, and that the dose-exposure is linear across a dose range of 100 mg to 400 mg QD derazantinib.

The available safety data with derazantinib across the dose range of 100 mg to 400 mg QD together with the revised assumption on dose-linearity and half-life of derazantinib, support the exploration of a higher dose of 400 mg per day (given as 200 mg BID) as an additional option to assess whether the benefit to risk profile may be further improved in mUC patients (Derazantinib Investigator's Brochure [IB] - Edition 9.0, dated 29 January 2021).

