3.2.2 Secondary endpoints

- DCR, as measured by the proportion of patients with confirmed CR, PR or stable disease (SD)¹ by BICR
- DOR, as calculated from the first date of documented tumor response to disease progression by BICR
- Median PFS and PFS at 6 months, as determined by BICR and measured from time of first dose to time of objective tumor progression or death, and the proportion of patients alive and free of objective tumor progression 6 months after cohort assignment, respectively
- Median OS and OS at 6 months, as measured from time of first dose until time of death and the proportion of patients alive 6 months after cohort assignment, respectively
- Safety and tolerability of study drugs as measured by the frequency and severity of AEs, clinical laboratory parameters, vital signs, ECOG PS, physical examinations (including eye examinations), and ECG parameters over time, and graded by NCI CTCAE 5.0
- Derazantinib (and – if applicable –derazantinib metabolites) plasma concentrations, C_{max} , t_{max} , AUC_{0-12} , AUC_{0-24} , AUC_{last} assessed by measurements in blood samples during treatment as monotherapy (Substudy 5) or in combination (Substudy 3)
- Changes in HR-QoL and symptom response, measured by global, functional and symptom scores obtained from patient reported outcome instruments at baseline and over time (EORTC QLQ C30, FACT-BI, EQ-5D [5L] VAS), and Health Transition Index/G-SET.

¹ Evaluating target lesions, SD is defined as neither sufficient shrinkage to qualify for PR nor sufficient increase to qualify for Progressive Disease (PD, see following definition), taking as reference the smallest sum of diameters while on study. PD is defined as at least a 20% increase in the sum of diameters of target lesions, taking as reference the smallest sum on study (this includes the baseline sum if that is the smallest on study). In addition to the relative increase of 20%, the sum must also demonstrate an absolute increase of at least 5 mm. (Note: the appearance of one or more new lesions is also considered progression).

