13. Tumor assessments performed as SoC prior to obtaining informed consent and within 28 days of the first dose of study treatment on C1D1 may be used rather than repeating tests. The first on-study tumor imaging assessments will be performed after 9 weeks on study, and will be repeated every 9 weeks (± 7) from C1D1 (i.e., at C4D1, C7D1, C10D1) and every 12 weeks (± 7) from C10D1 (i.e., at C14D1, C18D1, etc.) thereafter (with additional scans as clinically indicated and as per RECIST 1.1 criteria) until disease progression, death, or loss of follow-up. A tumor assessment should be performed at the End-of-Treatment visit only if the prior scan was not done within 4 weeks (28 days) prior to this visit, or if the prior scan did not show radiographic disease progression (see Sections 5.2.2.7 and 5.3.3.2). The same radiographic procedure as used at the SV must be used throughout the study for each patient to follow target lesions, and results must be reviewed by the Investigator before dosing at the next cycle. Imaging timing should be based on the first dose at C1D1, should follow calendar days, and should not be adjusted for delays in cycle starts.
14. For pre-dose PK blood sampling at C1D15 (**all substudies**), and C1D8, C2D8 and C2D15 (**safety interim analysis patients in Substudies 3 and 5**), administer derazantinib at the study site.
15. Derazantinib PK blood (plasma) sampling will be performed according to the following schedule:
 - a. **Rich PK profiling - Applicable to safety interim analysis patients in Substudy 3 and 5 only:**
 - C1D1, prior to derazantinib dose, and 1 hour (± 5 minutes), 2 hours (± 5 minutes), 4 hours (± 15 minutes), 8 hours (± 30 minutes), 10 hours (± 30 minutes), 12 hours (± 30 minutes; prior to the second dose administration), 24 hours after first derazantinib administration (i.e., 12 hours post second dose administration but within 1 hour prior to the third dose).
 - C1D8, pre-dose (within 1 hour prior to the next dose), and 6–8 hours after derazantinib administration.
 - C1D15, pre-dose (within 1 hour prior to the next dose), and 6–8 hours after derazantinib administration.

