8.3.6 Pharmacokinetic analysis

In the Rich derazantinib PK sampling population, PK parameters will be determined by non-compartmental analysis. The following parameters will be determined: C_{\max} , t_{\max} , AUC_{0-12} , AUC_{0-24} , AUC_{last} . PK parameters from rich PK sampling will be summarized by Substudy and Cohort using descriptive statistics. Derazantinib plasma concentrations at each nominal time-point will be summarized by substudy and cohort using descriptive statistics.

¹ Treatment emergent AEs (TEAE) are AEs not present prior to the start of study treatment, or AEs already present prior to the start of study treatment that worsen in either intensity or frequency following initiation of study drug treatment.

In the Sparse derazantinib PK sampling population, derazantinib plasma concentrations at each nominal time-point will be summarized by Substudy and Cohort using descriptive statistics.

In the atezolizumab PK population, atezolizumab and ADA serum concentrations at each nominal time-point will be summarized by Substudy and Cohort using descriptive statistics.

Population PK (PopPK) analyses may be performed with the possibility of pooling PK data from other clinical studies. Any PopPK analysis will be reported separately.

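### AUC0-24 and AUClast for the 200 mg BID regimens are to come from profiles with no sample between 12 h and 24 h; a standard trapezoid would read the Cycle 1 Day 1 values too low

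*Protocol*

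**What the plan says.** Protocol 5.3.4.1 states that the safety interim patients of Substudies 3 and 5 "will undergo rich PK sampling for measurement of plasma concentrations of derazantinib and relevant PK parameters". At C1D1 the times are pre-dose, 1, 2, 4, 8, 10 and 12 h, the last of these "prior to the second dose administration), 24 hours after first derazantinib administration". The 24 h sample is defined as "12-hour post second dose administration but within 1 hour prior to the third dose", so it is the trough of dose 2. C2D1 has the same pattern. Footnote 15a to Table 1 of the protocol and footnote 15a to Table 1 of the SAP repeat the schedule, so it is not a slip in one place.

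On analysis, Protocol 8.3.6 says: "In the Rich derazantinib PK sampling population, PK parameters will be determined by non-compartmental analysis". It names Cmax, tmax, AUC0-12, AUC0-24 and AUClast. Protocol 3.2.2 makes these secondary endpoints for the BID regimens, "assessed by measurements in blood samples during treatment as monotherapy (Substudy 5) or in combination (Substudy 3").

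SAP 6.5 leaves PK to a separate analysis plan that is not among the documents.

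**The concern.** AUC0-24 covers two doses, but only the first has a sampled absorption phase. The last sample of the profile is at 24 h, so AUClast covers the same interval and has the same gap. A straight line from the 12 h trough to the 24 h trough cuts off everything dose 2 adds above that line.

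On Day 1 a maximum taken over all the samples is also unsafe. If the drug falls little within 12 h, the 24 h trough carries two doses and can exceed the observed peak of dose 1. Cmax and tmax would then be read from a trough.

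Two secondary PK endpoints are directly at stake. PK data are also part of the joint safety interim review (Protocol 8.3.5.1), and Protocol 3.1.4 makes completion of Stage 1 in Substudy 5 depend partly on exposure.

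**Working it through.** The plan states no AUC or bias figure, so there is nothing of its own to reproduce.

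**Inputs from the documents.** Sample times 0, 1, 2, 4, 8, 10, 12 and 24 h, with doses at 0 and 12 h (Protocol 5.3.4.1). Protocol 1.4.3.1 says that "the half-life of derazantinib is in a range of 8 to 10 days compared to a previous assumption of only 5 days" and that exposure is linear from 100 to 400 mg QD.

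**Assumed, because the documents give no values.** First-order absorption rate ka; lag time; and, for two compartments, the share of the amplitude in the fast phase and the half-life of that phase.

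**Direction.** Let C1(t) be the single-dose curve. With linear kinetics:
- C(12) = C1(12) and C(24) = C1(12) + C1(24).
- The trapezoid's mean over 12-24 h is [C(12) + C(24)]/2 = C1(12) + C1(24)/2.
- The true mean is mean C1 over 0-12 h plus mean C1 over 12-24 h.

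The trapezoid is lower for any single-dose curve that is concave or peaks before about 12 h. Since C(24) - C(12) = C1(24) > 0, a linear-up/log-down rule also uses the straight line here.

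**One worked case.** One compartment, half-life 8 days (k = ln 2/192 = 0.00361 per h), ka = 1 per h, no lag, unit scale: C1(t) = ka/(ka - k) x [exp(-kt) - exp(-ka t)].
- C at 0, 1, 2, 4, 8, 10, 12 h: 0, 0.6308, 0.8606, 0.9709, 0.9747, 0.9680, 0.9611. C1(24) = 0.9203, so C(24) = 1.8814.
- Trapezoid 0-12 h: 0.315 + 0.746 + 1.832 + 3.891 + 1.943 + 1.929 = 10.66.
- Trapezoid 12-24 h: 12 x (0.9611 + 1.8814)/2 = 17.06. Total 27.71.
- Exact integrals of C1: 22.07 over 0-24 h and 10.78 over 0-12 h. True AUC0-24 = 22.07 + 10.78 = 32.85.
- Ratio 27.71/32.85 = 0.843, about 16% low. AUC0-12 is 10.66/10.78 = 0.988 of true.
- The largest sampled value is at 24 h (1.88, against 0.97 for the first peak).

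**Range, half-life 8-10 days, no lag unless stated.**

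| Case | Trapezoid AUC0-24 against true |
|---|---|
| C1D1, one compartment, ka 0.5-2 per h | 0.83-0.87 |
| C1D1, two compartments, 70-90% fast phase of 4-6 h, ka 0.5-2 | 0.68-0.80 |
| C1D1, one compartment, ka 0.1 / 0.2 | 6% / 9% low |
| C1D1, one compartment, 1 h lag | 4% to 15% low |
| C1D1, one compartment, 3 h lag | 9% low to 1% high |
| C1D1, one compartment, 6 h lag, ka 0.5 | 9% high |
| C1D1, two compartments, wider grid (50-95%, 2-12 h) | 11% to 39% low |
| C2D1, after 42 doses | about 1-7% low; up to 11% low in the wider grid |

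AUC0-12 from the same samples stays within about 2.5% of true in the no-lag cases.

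**Two better derivations from the same samples.**
- C1D1, superposition: AUC0-24 = 2 x AUC0-12 + 12 x [C1(12) + C1(24)]/2, with C1(12) = C(12) and C1(24) = C(24) - C(12). In the worked case: 2 x 10.66 + 12 x (0.9611 + 0.9203)/2 = 21.31 + 11.29 = 32.60, or 0.992 of true. Across the cases tried: 0.986-1.008.
- C2D1: 2 x AUC0-12 is 0.993-0.996 of true. Three weeks is only 21/10 = 2.1 to 21/8 = 2.6 half-lives, but all that is needed is that two successive 12 h intervals are nearly alike.

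**The case against.** **The separate PK plan may already deal with this.** It may, and no passage commits to a straight trapezoid. What stands is that the protocol fixes the method, the parameters and the sample times, and that nothing visible corrects for the gap. Local adaptation of the schedule (footnote in 5.3.4.1) and population PK (8.3.6) are both optional, and neither is said to replace these endpoints.

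**Day 1 AUC0-24 need not be lost.** This stands. A reader might infer that it cannot be estimated from these samples, but the linearity stated in Protocol 1.4.3.1 allows superposition. Only the plain trapezoid should go.

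**The decision impact is not documented.** This also stands. A reader might infer that the Substudy 5 exposure condition is biased against BID. Section 3.1.4 names neither AUC0-24 nor C1D1, and section 1.4.1.5 speaks of exposure reached within one or two weeks, for which C1D8 and C1D15 samples exist. Even an exact Day 1 AUC0-24 separates the regimens poorly. In the worked case, true 200 mg BID against 300 mg QD is 32.85/(1.5 x 22.07) = 0.99; the trapezoid would show 27.71/33.10 = 0.84. In the active substudies, patients on 300 mg QD are sparsely sampled, so they give no matching rich profile.

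**A 24 h tmax is not general.** A long terminal half-life does not show that concentrations hold up over 12 h if there is a distribution phase, and section 1.4.3.1 describes a two-compartment model. The 24 h reading occurs in every one-compartment case but only some two-compartment cases; with a 90% fast phase of 6 h and ka 0.5-2, the observed peak falls at 1-4 h.

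**Conclusion.** The point holds for the endpoint values. If the 12-24 h gap is bridged by a standard trapezoid, C1D1 AUC0-24 and AUClast for 200 mg BID are low by roughly 13-17% (one compartment) to 20-32% (two compartments). The direction follows from superposition unless absorption is markedly delayed. The size rests on assumed constants and should be read as a range. At C2D1 the loss is about 1-7% under the same assumptions. On Day 1, Cmax and tmax over 0-24 h may be read at the 24 h trough, depending on the distribution phase. AUC0-12 is adequately sampled at both visits.

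An effect on the Substudy 5 exposure decision is possible but not documented, since no metric is named.

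**What to change.** In Protocol 3.2.2 and 8.3.6 and in the separate PK plan, for patients on BID dosing at the visit:
- Derive Cmax, tmax and AUC over 0-12 h.
- At C2D1, report daily exposure as 2 x AUC0-12 and state the near-steady-state assumption, including uninterrupted dosing beforehand.
- At C1D1, do not report a plain-trapezoid AUC0-24 or AUClast. Either omit them or derive the 0-24 h value by the superposition formula above, with the linearity assumption stated.
- Otherwise use the 24 h sample as a trough.

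The limit to BID dosing at the visit matters because Table 4 allows reduction to once-daily dosing before C2D1; for those patients 0-24 h is a single dosing interval.

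The cost is one paragraph in each document and no extra blood draws. The downside is reliance on linearity at C1D1 and on near steady state at C2D1; the error was under 1.5% and under 1% respectively in the cases tried.
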